During the initial funding period of this grant, we tested the hypothesis that the volume and shape of the hippocampus could predict the outcome of treatment with donepezil in patients with very mild-to-mild DAT. The rationale for this experiment was that hippocampal neurons receive cholinergic afferent projections (Umbriaco, et al, 1995), and so became the indirect targets of cholinomimetic treatments. We now propose to extend this investigation of the relationships between neuroanatomical structure and treatment response in patients with DAT by 1) determining what neuroanatomical changes are most strongly correlated with the progression of cognitive deficits in patients with DAT (*Specific Aim 1*), and 2) determining whether treatment with cholinesterase inhibitors and/or adjunctive memantine can slow progression of the neuroanatomical and cognitive/behavioral changes associated with AD (*Specific Aim 2*).

The specific aims and hypotheses of the project are as follows:

Specific Aim 1:

To determine what neuroanatomical measures are most strongly correlated with the progression of cognitive deficits in patients with DAT, we propose to use high resolution magnetic resonance (MR) imaging and the tools of computational anatomy to assess changes in the structure of the hippocampus, parahippocampal gyrus and cingulate gyrus in subjects with very mild-to-mild DAT over two years. During the first funding period of this project, we collected data using MR imaging and large-deformation high dimensional brain mapping (HDBM-LD) that shows that progressive hippocampal volume loss and shape change discriminates subjects with very mild DAT from nondemented controls (see Progress Report). The volume, thickness, and surface area of the parahippocampal and cingulate gyri will be assessed in the proposed work using labeled cortical depth mapping (LCDM), a new computational tool that was developed during the last funding period (see Progress Report). (**Hypothesis 1: Over two years, decreases in hippocampal and cortical volumes, thinning of the cingulate and parahippocampal cortices, and changes in hippocampal shape will be correlated with the rate of cognitive decline in subjects with very mild-to-mild DAT. Moreover, in a stepwise regression**

model, each of these variables will predict the rate of cognitive decline in DAT subjects independently of each other and independently of the effects of age, gender and apoE allelic status.)

Specific Aim 2:

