There are two major areas of clinical significance to the proposed studies. First, the human study proposed in this application represent direct tests of the capacity of memantine and donepezil to slow the progression of DAT in patients. Second, we will be able to identify neuroanatomical measures that are most highly correlated for assessing the clinical progression of the AD process. By identifying neuroanatomical measures that are most sensitive to disease progression and to the potential effects of drug treatment, we will be identifying measures likely to be sensitive to the disease-altering effects of other therapeutic approaches to be developed in the future.

PRELIMINARY STUDIES

Discrimination of Subjects with Very Mild DAT and Controls Using Neuroanatomical Markers

To select neuroanatomical markers optimal for tracking the progression of disease in patients with DAT, one can first determine which neuroanatomical markers discriminate patients with early forms of DAT from controls. In our first study of this kind, we compared 18 subjects with very mild DAT and 18 elderly controls matched for age and gender using measures of hippocampal volume and shape generated by HDBM-LD (Csernansky, et al, 2000). The elderly subjects were categorized as having either very mild DAT (i.e. CDR 0.5) or no dementia (i.e., CDR 0) using the Clinical Dementia Rating Scale (CDR) ([name], 1993). MR scans from a younger control group previously recruited for a study of schizophrenia (Csernansky, et al, 1998) were included so that we could also assess the effects of aging alone on hippocampal structure. Measures of hippocampal volume and shape both discriminated the CDR 0.5 and CDR 0 subjects. There was no significant difference in hippocampal volume between the elder non-demented subjects and the younger control subjects; however, the shape of the hippocampus also discriminated these two groups. Interestingly, the patterns of hippocampal shape deformation that discriminated CDR 0.5 and CDR 0 subjects and the CDR 0 subjects from younger controls were markedly different, indicating that the neurobiological effects of early DAT and healthy aging on hippocampal structure were distinct.

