Variables to assess changes in structural volume, thickness, and shape (for the hippocampus) will be generated as described above. Bivariate correlations between changes in clinical and neuroanatomical variables will be estimated using non-parametric statistics (Spearman's rho). To assess whether observed bivariate relationships are independent of each other, a stepwise multiple regression model will be developed including all independent neuroanatomical variables and slope values for the CDR sum-of-boxes scores as the dependent variable.

To test **hypothesis 2** (*The rate of decreasing hippocampal and cortical volumes, thinning of the cingulate and parahippocampal cortices, and changing hippocampal shape will be equal in DAT subjects that are untreated and in DAT subjects that are treated with donepezil alone, but greater than the rate of volume loss, thinning and hippocampal shape change in DAT subjects that are treated with the combination of donepezil and*

memantine.), rates of change for the various neuroanatomical variables will be compared in DAT subjects that are untreated, that are treated with donepezil alone, that are treated with the combination of donepezil and memantine, and in nondemented comparison subjects. These analyses will be performed using simple difference scores (follow-up minus baseline) for volume and thickness variables. To compare rates of change in hippocampal shape across groups, a MANOVA using eigenvectors derived from the time 1-to-time 2 transformation covariance will be performed (see above). The distributional characteristics of each of these variables will be examined prior to hypothesis testing. Finally, non-parametric (Wilcoxon rank sum tests) statistics will be used to compare the groups.

i. Sample Size and Power Considerations

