Based upon previous work by our group in similar groups of CDR 0.5 and CDR 1 DAT subjects (Berg, et al, 1988; Berg, et al, 1992), and on our experience with the subjects recruited and studied during the initial funding period, we estimate that the attrition rate of subjects who cannot continue in the study for the full two years due to pronounced deterioration, drug side-effects, or refusal to participate will be approximately 20% or less, leaving at least 40 subjects who would provide data for the entire two-year period. However, the number of subjects entered into the analysis may exceed this somewhat, since a slope value can be estimated for each subject who remains in the treatment trial for at least five assessments (one year). Estimating 40 subjects are used in the analysis used to test **Hypothesis 1**, we will have a power of .80 to detect a correlation (or partial correlation) of .44 or more with a 2-tailed significance level of .05 (Borenstein and Cohen, 1988; Kraemer and Thiemann, 1987).

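### Aim 1 sets out to find which MR measures track decline best, but neither planned analysis compares the correlations or gives the uncertainty of their order

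*Combined protocol and SAP*

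**What the plan says.** The aim is comparative. Specific Aim 1 opens: "To determine what neuroanatomical measures are most strongly correlated with the progression of cognitive deficits in patients with DAT". The section on the clinical significance of the proposed studies repeats this as one of two areas of significance: "we will be able to identify neuroanatomical measures that are most highly correlated for assessing the clinical progression of the AD process". It adds that the measures found are likely to be useful for judging future disease-altering treatments.

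The analysis is in Study Design, h. Data Analysis, under Hypothesis 1. Its first step is: "Bivariate correlations between changes in clinical and neuroanatomical variables will be estimated using non-parametric statistics" (Spearman's rho). Its second step is a joint model: "a stepwise multiple regression model will be developed including all independent neuroanatomical variables and slope values for the CDR sum-of-boxes scores", with the slope as dependent variable. The purpose given for that model is "To assess whether observed bivariate relationships are independent of each other".

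The sample size section (i. Sample Size and Power Considerations) says "Estimating 40 subjects are used in the analysis used to test" Hypothesis 1, and on that number "we will have a power of .80 to detect a correlation (or partial correlation) of .44 or more" "with a 2-tailed significance level of .05".

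Hypothesis 1 itself claims that the measures correlate with decline and predict it independently. It does not claim an order among them.

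**The concern.** To say that some measures correlate more strongly with decline than others, one must compare correlations estimated on the same subjects. The plan has no test or interval for a difference between two correlations, no uncertainty for a rank, and no rule for calling a measure one of the strongest. The stepwise model does not fill the gap. Its first step simply takes the largest sample correlation, and its later steps ask whether a measure adds to those already chosen, which is a different question.

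Followed as written, the answer to Aim 1 would be read from the order of the observed rhos or from the order of entry into the model. With 40 subjects that order carries considerable error. At stake is one of the study's two stated products: the list of measures recommended for later trials of disease-modifying treatment.

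**Working it through.** **1. The plan's own figure.** Inputs from the sample size section: n = 40, r = .44, two-sided .05. By Fisher's z, power = Φ(atanh(.44) × √(40 − 3) − 1.96) = Φ(.472 × 6.083 − 1.96) = Φ(.91) = .82. With the usual variance adjustment for Spearman's rho it is .80. The stated .80 reproduces, but it concerns one correlation against zero.

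**2. Precision of one correlation.** The 95% interval around an observed .44 is tanh(.472 ± 1.96/6.083) = tanh(.472 ± .322) = .15 to .66. Most plausible competitors lie inside it.

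**3. How often the best measure comes first.** The documents give no true correlations, inter-correlations or final count of measures, so the following are assumptions. There are k measures with a common inter-correlation of .3 to .7. One has the higher true correlation with the decline slope and the rest are equal. Data are multivariate normal, Spearman's rho is used, and each setting has 4,000 to 10,000 simulated trials. The low count of six is hippocampal volume, two cortical volumes, two cortical thicknesses and one shape score. Ranges run across the inter-correlations.

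| True r, best v rest | k | n | Best ranks first |
|---|---|---|---|
| .44 v .34 | 6 | 40 | 37-50% |
| .50 v .35 | 6 | 40 | 50-69% |
| .44 v .24 | 6 | 40 | 60-81% |
| .44 v .14 | 6 | 40 | 81-96% |
| .44 v .34 | 10 | 40 | 27-38% |
| .44 v .24 | 10 | 40 | 50-73% |
| .44 v .34 | 6 | 100 | 54-72% |
| .44 v .24 | 6 | 100 | 85-98% |

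When all six measures have a true r of .40, the best observed rho averages .48-.53 and the best-to-worst gap averages about .21-.32 by chance.

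A hand check with two measures: the standard error of a difference between two such rhos at n = 40 is .12-.18, so a true gap of .10 gives a correct order with probability about Φ(.10/.18) = Φ(.56) = .71 to Φ(.10/.12) = Φ(.83) = .80. The simulated figure for k = 2 is 70-78%.

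**4. The stepwise model.** With six measures, n = 40 and entry at p < .05 (600 trials per setting), the best measure enters first in 38-48% of trials for .44 v .34 and 59-75% for .44 v .24. This is much the same as ranking the rhos.

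**5. Power of a direct comparison.** A two-sided .05 Williams test of two dependent correlations at n = 40 has power 9-14% for .44 v .34 and 20-42% for .44 v .24.

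**6. Which form of reporting works.** Bootstrapping subjects in simulated data (n = 40, six measures):
- With .50 v .35, the interval for the top measure minus the next excludes zero in only 0-3% of data sets.
- The bootstrap probability of ranking first, for the observed top measure, averages about .48-.53 when all six are equal and .55-.61 when one is truly better. It hardly tells the two cases apart.
- Unadjusted 95% intervals for observed best minus observed worst exclude zero in 37-40% of data sets when all six are equal. Intervals that ignore the selection would therefore mislead.

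**The case against.** The best defence is that the tested claim is not a ranking. Hypothesis 1 asks for correlation and independent prediction, and Spearman's rho followed by a multiple regression addresses both. That stands, and those tests are not faulted here. The comparative claim sits in the aim and the significance text, so narrowing that text would also close the gap.

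Three stronger readings are tempting, and the documents do not support them.
- A reader might infer that the plan only looks at each correlation in isolation. It does not: the stepwise model enters all the measures jointly.
- A reader might infer that the study promises one winning measure. Both places speak of measures in the plural, so a set is a legitimate answer.
- A reader might infer that the choice would be mostly sampling error. For .50 v .35 the best of six ranks first in 50-69% of trials, against 1/6 = 17% for a random pick. When measures are equal, choosing any of them costs nothing, and mistakes are commonest where the true gap is smallest.

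The simulation inputs can also be challenged, since none is in the documents. They cut both ways. Larger gaps make the problem small. But six is probably a low count: volume, thickness and surface area for two gyri make 6, hippocampal volume makes 7, and 12 eigenvector scores, as in the group's longitudinal study, make 19, before left and right sides are counted separately.

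Finally, the sample may exceed 40. The sample size section allows for somewhat more, and pooling all the DAT groups would give about 21 + 38 + 40 = 99 to 21 + 47 + 40 = 108. Pooling helps but does not remove the problem for a gap of .10 (54-72% at n = 100).

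**Conclusion.** The point holds in a limited form. The documents claim to identify the measures most closely related to decline, and no planned analysis compares the correlations or attaches uncertainty to their order. That much follows from the text alone. The size depends on assumed gaps, inter-correlations and number of measures. With six measures and 40 subjects, the measure at the top is not the truly best one in about half to five-eighths of trials for a gap of .10 (100 minus 37-50%) and about a fifth to two-fifths for a gap of .20 (100 minus 60-81%). For a gap of .30 the error is 4-19%. The consequence is an unsupported ranking in a headline conclusion. The tests of Hypothesis 1 and the stated power for a single correlation are not invalidated.

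**What to change.** In the Data Analysis section, under Hypothesis 1:

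1. Add bootstrap intervals, resampling subjects, for the pairwise differences in |rho| with the CDR sum-of-boxes slope. Make them simultaneous across all pairs; with six measures there are 6 × 5/2 = 15.
2. State in advance how hippocampal shape enters. It consists of several eigenvector scores, and a multiple correlation over them cannot be set beside a single rho. With 12 unrelated scores and n = 40, the expected R² is 12/39 = .31, an R of about .55 by chance.
3. Report the set of measures that cannot be separated from the top one.
4. Limit the conclusions for Specific Aim 1 and the clinical significance section to that set.

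Do not use a rule that names a single winner, or a bootstrap probability of ranking first. At this sample size the first almost never succeeds and the second suggests a winner even when none exists.

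The cost is a few lines of text and a short program, with no new data and no design change. The drawback is that the likely result is a broad set of measures. If the sponsor does not want the extra analysis, the alternative is to reword the aim and the significance text as estimation of each correlation, without comparative claims.

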Hippocampal volumes, total cerebral volumes and total intracranial volumes were not significantly correlated with any of the measures of cognitive decline. However, among the first 10 eigenvectors (which explained > 80% of the variance in hippocampal shape), eigenvector 3 coefficients were correlated with two measures of the rate of cognitive decline. More negative eigenvector 3 coefficient values were significantly correlated with increasing sum-of-boxes slope values ($r = -0.34$, $p = 0.03$, two-tailed) and with increasing NPI slope values ($r = -0.31$, $p = 0.05$, two-tailed). A trend correlation was observed between more negative eigenvector 3 coefficient values and decreasing MMSE total scores ($r = 0.29$, $p = 0.07$, two-tailed), but no correlation was observed between eigenvector 3 coefficient values and ADAS-Cog total scores ($r = -0.11$, $p = .50$, two-tailed). These correlations were unchanged after taking into account total cerebral brain volume, total intracranial volume, and age.

[figure not shown]

Figure 3. Pattern of Hippocampal Shape Variation Correlated with the Outcome of Donepezil Treatment.

The two panels illustrate the extremes of hippocampal shape variation in eigenvector 3, that were characteristic of DAT subjects who showed clinical worsening (top panel) and improvement (bottom panel) during donepezil treatment. Cooler colors (blue to purple) signify areas of inward deformation and warmer colors signify areas of outward deformation relative to the mean shape of all subjects.

The pattern of hippocampal shape variation represented by eigenvector 3 is shown in Figure 3. The pattern of shape variation associated with greater cognitive decline during donepezil treatment was similar to the pattern of shape deformation previously shown to discriminate CDR 0.5 and CDR 0 subjects (see Figure 1), and to be associated with disease progression changes CDR 0.5 subjects over time (see Figure 2) (i.e., inward deformation of the lateral prominence of the hippocampus). In turn, the relative absence of this pattern of deformation in hippocampal shape was associated a more favorable outcome during donepezil treatment. These results suggest that hippocampal shape may be a predictor of the capacity of DAT patients to respond to donepezil.

STUDY DESIGN

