A template image is prepared by an expert using manual outlining techniques, and includes, in this case, segmentation data for the total intracranial and brain volumes. The entire MR image of the template is first globally registered with the MR image of each target using a landmark-based transformation and scalar points at the boundaries of the brain and in the midline. An elastic transformation (with eight basis vectors having 2187 basis coefficients) is then performed, which matches the templates for the total intracranial space and total brain to the target. As with the transformations developed to study the hippocampus, the manifold and the elastic transformations used for this measurement are concatenated together and all the anatomical features of the segmented template brain are carried through the transformation.

h. Data Analysis

To test **hypothesis 1** (*Decreases in hippocampal and cortical volumes, thinning of the cingulate and parahippocampal cortices, and changes in hippocampal shape will be correlated with the rate of cognitive decline in subjects with very mild-to-mild DAT.*), growth curve models will be developed to assess the rate of cognitive decline for the principal (i.e., CDR sum-of-boxes scores) and secondary (i.e., ADAS-cog total scores, MMSE total scores, and NPI total scores) outcome variables (Laird and Ware, 1982). The underlying framework for the Laird and Ware model is essentially the same as for a traditional univariate repeated measures analysis of variance (ANOVA). However, the traditional ANOVA framework is difficult to apply when assessments are not available for all subjects at all time points. We have previously examined the advantages and disadvantages of this statistical model in characterizing rates of cognitive decline in a group of CDR 0.5 and CDR 1 DAT subjects highly similar to the one recruited for this project (Berg, et al, 1992). The CDR sum-of-boxes score was found to be entirely adequate as an outcome variable in that analysis (Berg, et al, 1992), because of its minimal ceiling and floor effects. The Laird and Ware model generates a slope value and intercept (i.e., estimate of baseline severity) for each subject.

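### Hypothesis 1 correlates at least six MR-change measures with four clinical slopes, with no primary MR measure, decision rule or multiplicity adjustment, and is sized for one unadjusted .05 correlation

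*Combined protocol and SAP*

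**What the plan says.** Section h, under the test of Hypothesis 1, first fits growth-curve slopes for the "principal (i.e., CDR sum-of-boxes scores) and secondary (i.e., ADAS-cog total scores, MMSE total scores, and NPI total scores) outcome variables". It then adds: "Bivariate correlations between changes in clinical and neuroanatomical variables will be estimated using non-parametric statistics (Spearman's rho"). A stepwise regression follows, to see whether the relationships found are independent of one another. Its only dependent variable is the CDR sum-of-boxes slope. Section b (Selection of Instruments for Clinical Evaluation) also ranks CDR sum-of-boxes as primary and the other three scales as secondary.

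The MR side is a list. Hypothesis 1 (Specific Aim 1) names volume changes in the hippocampus and cortex, thinning of two cortical regions, and hippocampal shape change. Section e keeps as many shape eigenvectors as explain roughly 75% of the variance, without fixing the number.

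Section i (Sample Size and Power Considerations) starts from 50 new subjects and expects that attrition "will be approximately 20% or less, leaving at least 40 subjects who would provide data for the entire two-year period". For Hypothesis 1 it claims "power of .80 to detect a correlation (or partial correlation) of .44 or more", "with a 2-tailed significance level of .05". No other significance level for Hypothesis 1 is given, and neither section h, section i nor the analysis text under Data Management mentions multiplicity.

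**The concern.** The clause is tested by many correlations, and the plan does not say which result decides it. One reader could accept a single eigenvector at p = .03 as support; another could require all the volume, thickness and shape measures to correlate. Both would be following the plan. On the first reading the false-positive rate for the clause is well above .05. On the second, the power stated for one correlation says little about the power of the hypothesis.

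The preliminary work shows that such grids get used. Under the heading on donepezil response, ten eigenvectors were set against four clinical slopes, and the report is that "eigenvector 3 coefficients were correlated with two measures of the rate of cognitive decline" (p = .03 and p = .05). At .05, 10 x 4 = 40 tests give 40 x .05 = 2 nominal hits on average when nothing is related.

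**Working it through.** **Inputs from the documents.** 40 subjects (50 x 0.8), two-sided .05 and r = .44 (section i). Four clinical slopes, one principal (section h). At least six MR measures (Hypothesis 1): hippocampal, parahippocampal and cingulate volume; parahippocampal and cingulate thickness; and hippocampal shape counted once. The group's longitudinal study needed 12 eigenvectors for 75% of the variance (Preliminary Studies), so entering eigenvectors singly gives 5 + 12 = 17.

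**Assumption.** The documents give no correlations among the MR measures or among the slopes. They are varied here from 0 to 0.9.

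**Step 1: the plan's own power.** With Fisher's z, power = Φ(atanh(r)·√(n − 3) − z), where z = 1.960 for two-sided .05.
atanh(.44) = 0.4722 and √37 = 6.083, so the product is 2.872. Then Φ(2.872 − 1.960) = Φ(0.912) = .82.
With a variance factor of 1.06 for Spearman's rho the result is .80. The stated figure is therefore reproduced, as that of one unadjusted test.

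**Step 2: false positives if the tests are independent.** The chance of at least one is 1 − .95^k.
- k = 6: 1 − .95^6 = 27%
- k = 17: 1 − .95^17 = 58%
- k = 6 x 4 = 24: 71%
- k = 17 x 4 = 68: 97%, with 68 x .05 = 3.4 false positives expected

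**Step 3: allowing for correlation.** Spearman tests were simulated with 40 subjects and no true association. A common correlation was set among the volume and thickness measures and, where all four slopes are used, among the slopes. Where a range appears, the lower end gives the shape score the same correlation as the other MR measures and the upper end makes it independent. In the 17-measure rows the eigenvector scores are independent. Simulation error is about one percentage point.

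| MR measures | Correlation | CDR slope only | All four slopes |
|---|---|---|---|
| 6 | 0 | 27% | 71% |
| 6 | 0.5 | 22-23% | 54-59% |
| 6 | 0.9 | 12-15% | 22-28% |
| 17 | 0 | 58% | 97% |
| 17 | 0.5 | 56% | 94% |
| 17 | 0.9 | 52% | 78% |

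Counting surface area (named in Specific Aim 1) or left and right sides separately adds further tests. At a low or moderate correlation that raises the rate.

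**Step 4: the all-must-correlate reading.** If each of six tests had power .80, the power for all six would be .80^6 = .26 if they were independent, and never above .80.

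**Step 5: the price of control.** At the Bonferroni level for six tests, .05/6 = .0083, z = 2.638.
- Power at r = .44: Φ(2.872 − 2.638) = Φ(0.234) = .59
- Correlation detectable with .80 power: tanh((2.638 + 0.842)/6.083) = tanh(0.572) = .52

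**The case against.** Several points on the other side stand.

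- **The scales are ranked.** CDR sum-of-boxes is principal and the other three are secondary, so a reader who treats all four slopes as equal and takes the right-hand column as the headline goes further than the text. The left-hand column is the fairer figure. It still exceeds .05 in every setting, because the ranking leaves the MR side open.
- **The per-test level is inferred.** Section h says the correlations will be estimated, and .05 appears only in section i. But they are listed under the test of Hypothesis 1, and section i sizes that test at .05.
- **The hypothesis can be read as requiring every measure.** It joins the measures with a conjunction, and its regression clause claims that each one predicts decline. That reading has no inflation. It is not stated as the rule for the correlation clause, however, and it conflicts with the .80 power claim.
- **Chance findings need not dominate.** A reader might infer that Aim 1 would report false markers more often than not. That requires every association to be null, whereas the Background cites work linking progressive volume loss to worsening. Even under the full null it fails for six measures on the CDR slope.
- **The preliminary result is not shown to be chance.** Both hits involve the same eigenvector, the trend and null results are reported too, and the conclusion is hedged. That analysis also used shape at one time point, not change in shape.

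A single deciding hippocampal-volume test would also be too narrow a remedy, because Aim 1 asks which measures relate most strongly to decline.

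**Conclusion.** The concern holds in a limited form. The plan names no primary MR measure, leaves the number of shape variables open, and gives no decision rule and no multiplicity adjustment, while its power statement covers one unadjusted correlation.

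If any single significant correlation counts and nothing is related, the false-positive rate on the principal slope is at least about twice the nominal .05 (about 12%, six measures correlated at 0.9) and may reach about 58% (seventeen independent measures). The four-slope range of about 22-97% is too dependent on unknown correlations to be quoted as one figure. The false-positive rates rest on the any-one reading, on .05 per test taken from section i, and on the assumed correlations. They depend little on the sample size, since each test roughly keeps its own level whatever n is.

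This should be corrected in the analysis text. It does not call the design or data collection for Aim 1 into question.

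**What to change.** In section h:

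1. Define the confirmatory family for the correlation clause as the volume and thickness changes plus one global hippocampal-shape test (that the retained eigenvector coefficients are jointly unrelated to the slope). Test each against the CDR sum-of-boxes slope, Holm-adjusted at two-sided .05. If the sponsor prefers, one MR measure named in advance may be tested first.
2. Fix what makes up the family: left and right combined or separate, one thickness percentile, and the rule for how many eigenvectors are kept.
3. State whether one adjusted result, or all of them, is needed to support the clause.
4. Label all ADAS-Cog, MMSE, NPI and single-eigenvector correlations exploratory.

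In section i, say that .80 power at .44 applies to a single unadjusted correlation. Add that at the strictest six-test level (.0083) power at .44 is about .59 and the correlation detectable with .80 power is about .52. If the all-must-correlate rule is chosen, give the power for that rule instead.

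The change is to wording only, with no new subjects, scans or visits. The cost is a stricter threshold and lower stated power for the individual correlations.
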